10.1.8. Source Documents

- Source documents provide evidence for the existence of the participant and substantiate the integrity of the data collected. Source documents are filed at the Investigator's site.

- Data reported on the CRF or entered in the eCRF that are transcribed from source documents must be consistent with the source documents or the discrepancies must be explained. The Investigator may need to request previous medical records or transfer records, depending on the study. Also, current medical records must be available.
- Definition of what constitutes source data can be found in the Study Manual.
- The Investigator must maintain accurate documentation (source data) that supports the information entered in the CRF.
- Study monitors will perform ongoing source data verification to confirm that data entered into the CRF by authorized site personnel are accurate, legible, complete, original, attributable, and verifiable from source documents; that the safety and rights of participants are being protected; and that the study is being conducted in accordance with the currently approved protocol and any other study agreements, ICH GCP, and all applicable regulatory requirements.

10.1.9. Study and Site Start and Closure

10.1.9.1. First Act of Recruitment

The study start date is the date on which the clinical study will be open for recruitment of participants.

The first act of recruitment is the activation of the first open site in the Interactive Response System (IRS) and will be the study start date.

10.1.9.2. Study/Site Termination

The Sponsor or designee reserves the right to close the study site or terminate the study at any time for any reason at the sole discretion of the Sponsor. Study sites will be closed upon study completion. A study site is considered closed when all required documents and study supplies have been collected and a study-site closure visit has been performed.

The Investigator may initiate study-site closure at any time, provided there is reasonable cause and sufficient notice is given in advance of the intended termination.

Reasons for the early closure of a study site by the Sponsor or Investigator may include but are not limited to:

For study termination:

- Discontinuation of further study intervention development

For site termination:

- Failure of the Investigator to comply with the protocol, the requirements of the IRB/IEC or local health authorities, the Sponsor's procedures, or GCP guidelines
- Inadequate or no recruitment (evaluated after a reasonable amount of time) of participants by the Investigator
- Total number of participants included earlier than expected

If the study is prematurely terminated or suspended, the Sponsor shall promptly inform the Investigators, the IECs/IRBs, the regulatory authorities, and any contract research organization(s) used in the study of the reason for termination or suspension, as specified by the applicable regulatory requirements. The Investigator shall promptly inform the participant and should assure appropriate participant therapy and/or follow-up

10.1.10. Publication Policy

Following completion of the study, the data may be considered for publication in a scientific journal and/or for reporting at a scientific meeting. Each Investigator is obligated to keep data pertaining to the study confidential. The Investigator must consult with the Sponsor before any study data are submitted for publication. The Sponsor reserves the right to deny publication rights until mutual agreement on the content, format, interpretation of data in the manuscript, and journal selected for publication are achieved.

10.2. Appendix 2: Clinical Laboratory Tests

- The tests detailed in Table 5: Protocol-Required Safety Laboratory Tests will be performed by the central laboratory.
- Local laboratory results are only required in the event that the central laboratory results are not available in time for either study intervention administration and/or response evaluation. If a local sample is required, it is important that the sample for central analysis is obtained at the same time. Additionally, if the local laboratory results are used to make either a study intervention decision or response evaluation, the results must be recorded.
- Protocol-specific requirements for inclusion or exclusion of participants are detailed in [Section 5](#) of the protocol.
- Additional tests may be performed at any time during the study as determined necessary by the Investigator or required by local regulations.

Table 5: Protocol-Required Safety Laboratory Tests

Clinical Chemistry Panel (Central Laboratory)

Alanine aminotransferase	Albumin
Alkaline phosphatase	Amylase
Aspartate aminotransferase	Bicarbonate
Blood urea nitrogen	Calcium
Chloride	Creatine kinase
Creatinine	Direct bilirubin Gamma-glutamyl transferase
Glucose	Inorganic phosphorus
Lactate dehydrogenase	Lipase
Potassium	Sodium
Total bilirubin	Total protein
Uric acid	

Hematology (Central Laboratory)

Hematocrit	Hemoglobin
Platelets	Red blood cell count
White blood cell count and differential [1]	

1. Manual microscopic review is performed only if white blood cell count and/or differential values are out of reference range.

Viral Load in Blood and Urine (Central Laboratory)

Adenovirus	BK virus
Cytomegalovirus	Epstein-Barr virus
Human herpesvirus 6	JC virus

When viral load determination is performed in the laboratory, residual viral deoxyribonucleic acid (DNA) will be stored for potential viral sequencing and genotyping in the event of recurrent infection.

Viral load determination at screening may be performed at a local or central laboratory for the purpose of determining eligibility/inclusion. If the results from the local laboratory are used for determination of eligibility/inclusion, an additional pre-randomization sample for viruria testing must be collected for assay at the central laboratory. These results do not have to be available at the time of randomization or study treatment infusion. Additional post-infusion samples may be collected, as clinically indicated.

Urinalysis (Local Laboratory)

Bilirubin	Blood
Glucose	Ketones
Leukocyte esterase	Nitrite pH
Protein	Specific gravity
Urobilinogen	

Stool Specimen (Central Laboratory)

Adenovirus	Cytomegalovirus
------------	-----------------

If a stool specimen is clinically indicated, stool samples will also be sent to the central laboratory for research purposes.

Cerebrospinal Fluid Sample (Central Laboratory)

Cytomegalovirus
Human

herpesvirus 6 JC virus

If a cerebrospinal fluid sample is clinically indicated, samples will also be sent to the central laboratory for research purposes as feasible. Cerebrospinal fluid samples required for clinical care of the patient take precedence over these research-related evaluations.

Other Laboratory Assessments

Serum pregnancy test [1]	Urine pregnancy test [1]
Follicle-stimulating hormone [2]	Peripheral blood mononuclear cells (PBMCs) and plasma [3]

Serology (HIV antibody, hepatitis B surface antigen [HBsAg], and hepatitis C virus antibody) along with confirmatory tests if requested

Virus Specific T-cell Assessment

1. For female patients of childbearing potential only. A serum (β -human chorionic gonadotropin) pregnancy test will be performed at screening. A urine pregnancy test will be performed prior to dosing for female patients who are of childbearing potential.
2. Follicle-stimulating hormone will be tested at screening for women of nonchildbearing potential who are postmenopausal, defined as 12 consecutive months with no menses without an alternative medical cause.
3. At each time-point indicated in the SoAs (Section 1.3), blood will be collected into a cell separation tube and processed to generate a PBMC fraction and a plasma fraction. Genomic DNA will be extracted from the PBMC fraction. The genomic DNA from PBMC and plasma fractions will be cryopreserved for potential future evaluation of virus-specific T cell persistence (PBMC fraction) and for future evaluation of cytokines and/or other humoral markers of inflammation/immune function (plasma fraction).

Investigators must document their review of each laboratory safety report.

10.3. Appendix 3: AEs and SAEs: Definitions and Procedures for Recording, Evaluating, Follow-up, and Reporting

10.3.1. Definition of AE

AE Definition

- An AE is any untoward medical occurrence in a clinical study participant, temporally associated with the use of study intervention, whether or not considered related to the study intervention.
- NOTE: An AE can therefore be any unfavorable and unintended sign (including an abnormal laboratory finding), symptom, or disease (new or exacerbated) temporally associated with the use of study intervention.

• Definition of Unsolicited and Solicited AE

- An unsolicited adverse event is an adverse event that was not solicited using a Participant Diary and that is communicated by a participant who has signed the informed consent. Unsolicited AEs include serious and non-serious AEs.
- Potential unsolicited AEs may be medically attended (ie, symptoms or illnesses requiring a hospitalization, or emergency room visit, or visit to/by a health care provider). The participant will be instructed to contact the site as soon as possible to report medically attended event(s), as well as any events that, though not medically attended, are of participant concern. Detailed information about reported unsolicited AEs will be collected by qualified site personnel and documented in the participant's records.
- Unsolicited AEs that are not medically attended nor perceived as a concern by participant will be collected during interview with the participant and by review of available medical records at the next visit.
- Solicited AEs are predefined local and systemic events for which the participant is specifically questioned, and which are noted by the participant in their diary.

Events Meeting the AE Definition

- Any abnormal laboratory test results (hematology, clinical chemistry, or urinalysis) or other safety assessments (eg, ECG, radiological scans, vital signs measurements), including those that worsen from baseline, considered clinically significant in the medical and scientific judgment of the Investigator (ie., not related to progression of underlying disease).
- Exacerbation of a chronic or intermittent pre-existing condition including either an increase in frequency and/or intensity of the condition.
- New conditions detected or diagnosed after study intervention administration even though it may have been present before the start of the study.
- Signs, symptoms, or the clinical sequelae of a suspected intervention- intervention interaction.
- Signs, symptoms, or the clinical sequelae of a suspected overdose of either study intervention or a concomitant medication. Overdose per se will not be reported as an AE/SAE unless it is an intentional overdose taken with possible suicidal/self-harming intent. Such overdoses should be reported regardless of sequelae.

Events NOT Meeting the AE Definition

- Any clinically significant abnormal laboratory findings or other abnormal safety assessments which are associated with the underlying disease, unless judged by the Investigator to be more severe than expected for the participant's condition.
- The disease/disorder being studied or expected progression, signs, or symptoms of the disease/disorder being studied, unless more severe than expected for the participant's condition.
- Medical or surgical procedure (eg, endoscopy, appendectomy): the condition that leads to the procedure is the AE.
- Situations in which an untoward medical occurrence did not occur (social and/or convenience admission to a hospital).
- Anticipated day-to-day fluctuations of pre-existing disease(s) or condition(s) present or detected at the start of the study that do not worsen.

10.3.2. Definition of SAE

An SAE is defined as any serious adverse event that, at any dose:
a. Results in death
b. Is life-threatening The term 'life-threatening' in the definition of 'serious' refers to an event in which the participant was at risk of death at the time of the event. It does not refer to an event, which hypothetically might have caused death, if it were more severe.
c. Requires inpatient hospitalization or prolongation of existing hospitalization 
• In general, hospitalization signifies that the participant has been admitted (usually involving at least an overnight stay) at the hospital or emergency ward for observation and/or treatment that would not have been appropriate in the physician's office or outpatient setting. Complications that occur during hospitalization are AEs. If a complication prolongs hospitalization or fulfills any other serious criteria, the event is serious. When in doubt as to whether "hospitalization" occurred or was necessary, the AE should be considered serious.• Hospitalization for elective treatment of a pre-existing condition that did not worsen from baseline is not considered an AE.
d. Results in persistent or significant disability/incapacity 
• The term disability means a substantial disruption of a person's ability to conduct normal life functions.• This definition is not intended to include experiences of relatively minor medical significance such as uncomplicated headache, nausea, vomiting, diarrhea, influenza, and accidental trauma (eg, sprained ankle) which may interfere with or prevent everyday life functions but do not constitute a substantial disruption.
e. Is a congenital anomaly/birth defect
f. Is a suspected transmission of any infectious agent via an authorised medicinal product
g. Other situations: 
• Medical or scientific judgment should be exercised by the Investigator in deciding whether SAE reporting is appropriate in other situations such as significant medical events that may jeopardize the participant or may require medical or surgical intervention to prevent one of the other outcomes listed in the above definition. These events should usually be considered serious.
○ Examples of such events include invasive or malignant cancers, intensive treatment for allergic bronchospasm, blood dyscrasias, convulsions or development of intervention dependency or intervention abuse.

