6.1. Study Intervention(s) Administered

[figure not shown]
ALVR105 is a third-party, donor-derived, “off-the-shelf,” VST product with specificity for BKV, AdV, CMV, EBV, and HHV-6 (with additional cross-reactive specificity for JCV) that is [REDACTED] and ready for immediate use. The Control Arm will receive IV infusions of [REDACTED] (without cells) as placebo.

Arm Name	Treatment (Cohort A and B and OL)	[REDACTED]
Intervention Name	ALVR105	[REDACTED]
Type	Drug	[REDACTED]
Dosage formulation	Ampule (Cryovial)	[REDACTED]
Unit dose strength(s)	[REDACTED]	[REDACTED]
Dosage Level(s)	[REDACTED] (<40 kg) or [REDACTED] (\geq 40 kg) dosed Q14D	[REDACTED]
Route of Administration	IV slow push [REDACTED]	[REDACTED]
Use	Experimental	[REDACTED]
Sourcing	Provided centrally by Sponsor	[REDACTED]
Packaging and Labeling	Study Intervention will be provided in cryovials. Each cryovial will be labeled as required per country requirement	[REDACTED]
Current/Former Name(s) or Alias(es)	ALVR105	[REDACTED]

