6.1.1. Cell Line Selection

ALVR105 cell lines will be selected for each patient based on an overall HLA match with 2 shared alleles set as a minimum threshold as outlined below. The HLA alleles used for evaluation of matching are HLA-A, HLA-B, HLA-DR, and HLA-DQ. The same cell line should be used for all infusions.

The appropriate drug product (ie, the cell lines for infusion) for patient administration will be selected

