6.2.2. Storage and Accountability

ALVR105 (or placebo) is stored in the vapor phase of liquid nitrogen in a continuously monitored storage freezer.

After investigational medicinal product (IMP) accountability and reconciliation procedures have been followed, all material containing ALVR105 (or placebo) will be treated and disposed of as hazardous waste in accordance with governing regulations and clinical site procedures.

ALVR105 and placebo accountability are the responsibility of the Principal Investigator and Sponsor. However, this responsibility may be delegated to a suitably qualified Investigator who has had appropriate study-specific training that has been documented. The Sponsor will maintain records that will allow anonymous traceability of each ALVR105 cell line to the third-party PBMC donor from whom it originated. These records will be maintained for 30 years after expiry for each cell line.

Detailed records will be maintained to allow for accurate accountability of ALVR105 and placebo as per applicable Sponsor and clinical site procedures. For further details and specifications, see the Cell Handling Manual.

[REDACTED]

[REDACTED]	[REDACTED]
------------	------------

[REDACTED]

[REDACTED]

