8.5.7.1. Special Situation Reports

Special situation reports include reports of overdose, misuse, abuse, medication error, and reports of adverse reactions associated with product complaints.

- **Overdose:** Refers to the administration of a quantity of a medicinal product given per

administration or cumulatively (accidentally or intentionally), which is above the maximum recommended dose according to the protocol. Clinical judgement should always be applied. In cases of a discrepancy in the drug accountability, overdose will be established only when it is clear that the patient has taken additional dose(s) or the Investigator has reason to suspect that the patient has taken additional dose(s).

- **Misuse:** Refers to situations where the medicinal product is intentionally and inappropriately used in a way that is not in accordance with the protocol instructions or local prescribing information and may be accompanied by harmful physical and/or psychological effects.
- **Abuse:** Is defined as persistent or sporadic, intentional excessive use of a medicinal product, which is accompanied by harmful physical or psychological effects.
- **Medication error:** Is any unintentional error in the prescribing, dispensing, or administration of a medicinal product by a healthcare professional, patient, or consumer, respectively. The administration or consumption of the unassigned treatment and administration of an expired product are always reportable as medication errors; cases of patients missing doses of investigational product are not considered reportable as medication errors.
- **Product complaint:** Is defined as any written, electronic, or oral communication that alleges deficiencies related to the identity, quality, durability, reliability, safety, effectiveness, or performance of a drug or device after it is released for distribution. A Special Situations Report Form will only be completed if a complaint is associated with an adverse drug reaction.

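### SAE criterion f makes suspected transmission of infection automatically serious only for authorised products, so read literally it leaves out ALVR105, the product this trial infuses

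*Protocol*

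**What the plan says.** Protocol 10.3.2 lists the SAE criteria a to g. Criteria a to e turn on outcome: death, threat to life, hospitalization, disability, birth defect. Criterion f turns on suspicion alone: "Is a suspected transmission of any infectious agent via an authorised medicinal product". Criterion g is the catch-all and begins: "Medical or scientific judgment should be exercised by the Investigator in deciding whether SAE reporting is appropriate in other situations". It goes on to describe significant medical events that could endanger the participant or need intervention, and says they should usually be regarded as serious.

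On the product, Protocol 6.1 states that "ALVR105 is a third-party, donor-derived", and its table gives the use as experimental. Protocol 6.2.2 handles ALVR105 under the accountability procedures for an investigational medicinal product, and has the sponsor keep records that allow "anonymous traceability of each ALVR105 cell line to the third-party PBMC donor from whom it originated".

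On other reporting routes, Protocol 8.5.7 limits adverse events of special interest to infusion-related events, GVHD and CRS; SAP 3.5.2 names these and adds graft failure to its list of summaries. Protocol 8.5.7.1 says: "Special situation reports include reports of overdose, misuse, abuse, medication error, and reports of adverse reactions associated with product complaints".

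**The concern.** The protocol did not leave transmission of infection to general judgment. It gave it a criterion of its own, triggered by suspicion, and then worded that criterion around authorised products. In a trial whose test product is an unauthorised, donor-derived cell therapy given to recent transplant recipients, transmission through a commercial product would be serious by rule. Transmission through the study product would need an outcome or a judgment to become so.

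What is at stake is reporting. SAE status drives the 24-hour deadline (Protocol 8.5.1 and 10.3.4), expedited reporting of unexpected related events (8.5.4.1), the SAE and treatment-emergent SAE tables (SAP 3.5.1), the SAE summaries sent to the DSMB (SAP 3.6), and the duty to notify events learned of after participation ends (8.5.1 and 10.3.4).

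**Working it through.** There is no figure in the plan to reproduce. The check sets the provisions side by side and asks which of them reaches a suspected transmission of an infectious agent through ALVR105.

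| Provision | Does it reach transmission through ALVR105? |
|---|---|
| 10.3.2, criteria a to d | Yes, if the event causes death, threat to life, hospitalization or disability |
| 10.3.2, criterion e | Not relevant |
| 10.3.2, criterion f | No, on its literal wording: ALVR105 is an investigational product (6.1, 6.2.2), not an authorised one |
| 10.3.2, criterion g | Often, with a default towards serious, but only if the investigator judges that the event may endanger the patient or need intervention; its examples do not mention transmission |
| 8.5.7 and SAP 3.5.2, events of special interest | Not named; an infusion-related event might overlap |
| 8.5.7.1, special situations | Not named; may enter as a product complaint, but the form is required only when an adverse drug reaction is associated |
| Section 8, general rules | Immediate safety concerns go to the sponsor at once, whatever their SAE status |
| 8.4.4 and 10.3.3, AE recording | Clinically significant laboratory changes are recorded as AEs, and every AE gets a causality assessment |

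Taking the cases in turn:

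1. **Severe transmission.** Criteria a to d apply. Criterion f is not needed.
2. **Symptomatic but not severe.** Criterion g usually applies. Where an adverse reaction is alleged against the product, the product-complaint route also carries a 24-hour deadline.
3. **Mild, asymptomatic or laboratory-only.** Criteria a to e do not apply. Criterion g applies only if the investigator sees danger or a need for intervention. The complaint form is not triggered without an adverse reaction. Criterion f, the only rule based on suspicion alone, excludes the product.

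The third case is the residual gap. If recorded as a non-serious AE, such an event would still appear among the AEs, and among the treatment-emergent AEs if it began after the first dose. It would not be in the SAE or treatment-emergent SAE tables or the SAE summaries to the DSMB. It would have no stated 24-hour deadline as an SAE. If recognised only after participation ended, it would carry no stated duty to notify, since 8.5.1 and 10.3.4 speak of SAEs there.

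**The case against.** The best defence is that the plan has other cover. Criterion g leans towards serious, and a suspected infection from infused cells in a patient soon after allogeneic transplant fits it readily. Section 8 requires immediate safety concerns to be discussed with the sponsor at once, precisely to decide whether study treatment continues. A suspected contaminated cell line is an alleged quality or safety deficiency, so Section 8.5.7.1 can apply. The DSMB is to monitor safety routinely and also reviews events of special interest (SAP 3.5.2 and 3.6); its full scope lies in a charter outside these documents. All of this stands and is why the gap is narrow. It does not close it: each route needs a judgment, an adverse reaction, or a category that does not name the event.

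A reader might also infer a larger harm from the dosing schedule. Tables 2 and 3 mark infusions on Day 1 and at Weeks 2, 4, 6, 8, 10 and 12, which is 7, and Protocol 6.1.1 says: "The same cell line should be used for all infusions". It is tempting to conclude that an unreported suspicion after the first infusion leads to 7 - 1 = 6 further exposures. The documents do not support that. No rule on stopping infusions (7.1, 9.5.1.1) depends on criterion f. The study halt (9.5.1.2) requires Grade 3, so a mild event would not count even if it were an SAE. The duty in Section 8 to raise safety concerns applies in any case. Rewording f would improve reporting; it would not in itself prevent an infusion.

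**Conclusion.** The point holds as a wording gap of minor severity. Read literally, criterion f does not cover ALVR105, and a mild, asymptomatic or laboratory-only suspected transmission from the cells is not automatically an SAE. The conclusion rests on the literal reading of authorised and on the protocol's own treatment of ALVR105 as investigational. The documents give no event rate, so I attach no number to how often the gap would matter.

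Three further readings go beyond the documents:

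- That transmission from the cells can never be an SAE. Criteria a to d and g rule this out.
- That the 30-year donor records in 6.2.2 exist for this event. The section gives the retention period and no purpose.
- That the exclusion in 10.3.1 of the disease under study from the AE definition makes this point larger. It might leave out a target virus suspected to come from the cells, but it is a separate matter. An SAE must first be an AE, so rewording criterion f would not clearly cure it.

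**What to change.** In Protocol 10.3.2, replace the closing words of criterion f, from the word via onward, with *via the study intervention or any other medicinal product*. Make the same change on the SAE form. Transmission through the test product then has the same automatic status as transmission through any other product.

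The cost is a few words in the protocol and on the form, and possibly a few more expedited reports. Dosing, patient management and the planned analyses do not change.
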